9.0 Study Withdrawal/Discontinuation

Individuals who wish to withdraw from the study may do so at any time by contacting the Principal Investigator ([name]) in writing without penalization or change to their medical care. Any data collected prior to withdrawing from the study will be analyzed as enrolled unless requested for full withdrawal by the participant. The PI and study personnel withhold the right to withdraw participants from the study if they are non-compliant with study procedures or if there is a perceived imminent medical threat to the participant.

10.0 Statistical Considerations

This pilot project is intended to create infrastructure, establish feasibility, and provide necessary preliminary data to design and conduct a prospective pilot RCT comparing precision smoking cessation treatment to usual care. As such, the primary outcome is feasibility and the study is not powered to detect differences between treatment groups for smoking cessation. However, we will conduct descriptive and exploratory analyses of collected data as well as assess for between-group differences in this clinical outcome.

Aim 1: Survey up to 1400 TN and MS SCCS smokers to assess attitudes and beliefs on smoking-related health risk perceptions, precision smoking treatment, and willingness to engage in a smoking cessation trial of PC. We anticipate a response rate of up to 70% of contacted participants.

Primary Analysis: Analysis of survey data will utilize the following general strategies: to test statistical differences in the frequency distributions of variables of interest, we will calculate t-tests for continuous parameters of interest, and chi-square tests for categorical parameters of interest. Participants will be categorized according to objective and subjective classifications of smoking-related disease risks. The objective measurement of lung cancer risk will be calculated using the validated PLCO_{M2012} model (Tammemagi NEJM 2013). Subjective measures of disease risks will be obtained via participant response to the study survey, as to whether the participant believes their risks for heart attack, cancer or lung cancer are lower, about the same, or higher than other smokers their age. Pearson correlation coefficients will be calculated to evaluate the relation between objective and subjective lung cancer risk estimates. Regression analyses will be used to calculate risk ratios and 95% confidence intervals for the associations between objective lung cancer risk, subjective disease risks, and use of smoking cessation aids or interest in precision smoking treatment. Regression statistical models will include variables for potential confounders such as age, race, sex, education, alcohol intake, and family history of lung cancer diagnosis in a first degree relative. P-values for trend tests will be calculated by treating ordinal variables as continuous in statistical models. Potential interactions will be evaluated by completing likelihood ratio tests comparing statistical models with and without the addition of cross-product terms.

Aim 3: Conduct a 3-arm RCT (Figure 2) to pilot PC interventions for feasibility and to determine preliminary estimates of biochemically-validated smoking cessation at 6 months vs. GBC.

Hypothesis: PC interventions will be acceptable to participants and feasible to administer.

Secondary hypotheses (exploratory): Compared to GBC, PC participants will exhibit higher smoking cessation and lung cancer screening rates.

Primary Analysis: We will assess engagement in smoking cessation treatment as measured by: (1) connection with the study tobacco treatment counselor, (2) connection with the state quitline and (3) use of study-provided medication. We will also obtain preliminary estimates of behavior change at 6 months, including: 1) biochemically-validated smoking cessation and 2) rates of lung cancer screening

[figure not shown]
for individuals who meet screening criteria. We will also collect information on process measures such as enrollment, educational material format, and costs per patient treated. Note, the current pilot RCT will not be powered to demonstrate significant differences in cessation rates by study group.

Privacy/Confidentiality Issues

Participant data will be collected using password protected and encrypted computers, and electronic participant tracking spreadsheets stored on a secure server. All paper records will be locked in secure areas and accessible to study staff only. To prevent the loss of data, all electronic information is password protected on anti-virus software enabled computer systems. Only study staff will have access to the study data on Shared File Areas. A participant number will identify all participants on study forms and in the database. Participant names and contact information will be stored in a separate file.

Protected Health Information (PHI) will be used in this study. The investigators will comply with the patient privacy guidelines of Vanderbilt University Medical Center and the rules outlined by the Health Insurance Portability and Accountability Act (HIPAA). Surveys will be associated with a participant number and all patient identified information will be managed by the SCCS offices in Jacksonville, FL, where they will be stored. The

Figure 2: Aim 3 - Pilot RCT: PC-Respiragene vs. PC-NMR vs. Guideline-based Care (GBC)

Survey Research Shared Resource will receive identified information in order to make necessary phone calls; study staff associated with Vanderbilt, Meharry, and TSU will receive only de-identified data files.

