2.0 Rationale and Specific Aims

Biologically informed precision treatment could benefit smokers in several ways. Biological tailoring may increase the salience of messaging about smoking-related disease and advice to quit. This in turn could reduce the optimistic bias, a tendency to underestimate one's own health risk, which hinders cessation efforts⁹, thereby increasing motivation to quit. Data has demonstrated that the nicotine metabolite ratio (NMR), a biomarker reflecting CYP2A6 activity, can inform choice of smoking cessation pharmacotherapy, such that "fast/normal" metabolizers are twice as likely to quit smoking on varenicline compared to "slow" metabolizers⁶. Additionally, smokers who are presented results from a commercially available, gene-based lung cancer risk assessment, Respiragene, are more likely to undergo lung cancer screening¹⁰⁻¹³. Respiragene recipients were also more likely to use nicotine replacement therapy (NRT) and quit smoking^{5,14-16}. Though promising tools to help engage smokers in cessation treatment, these individual, biologically informed feedback interventions have not yet been studied in community smokers in the US.

Our overarching aim is to leverage the SCCS and the U54 Community Outreach Core Community Advisory Board (CAB) to guide the development of two precision care (PC) interventions for smoking cessation: PC-NMR and PC-Respiragene. Both will be tailored to attitudes and beliefs of low socioeconomic status (SES) community smokers in the southeastern US, where tobacco use prevalence is one of the highest in the country. PC is rooted in the PRIME Model of behavior change¹⁷⁻¹⁹, which reflects a multi-faceted view of motivation for tobacco cessation. We will assess feasibility of PC in SCCS participants who smoke and conduct a 3-arm randomized controlled trial (RCT) to determine preliminary estimates of PC interventions vs. standard guideline-based care (GBC) on engagement^{4,20}, smoking cessation, and likelihood of undergoing recommended lung cancer screening if eligible²¹. Our hypothesis is that, compared to GBC, PC participants will exhibit higher smoking cessation and lung cancer screening rates. These effects will be explained by lower optimistic bias, higher self-efficacy and motivation to quit, and use of proven quit aids (medication, behavior therapy via state quit line).

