To accomplish our aim, daily smokers who are SCCS participants and providers at SCCS Community Health Centers (CHC), in Mississippi or Tennessee will be surveyed to assess their attitudes and beliefs about precision smoking treatment. Survey results will inform CAB-guided development of the PC study interventions. PC interventions will then be piloted in a RCT of up to 100 SCCS daily smokers willing to make a quit attempt with medication and be randomized 1:1:1 to PC-NMR, PC-Respiragene, or GBC and followed for 6 months. All RCT participants are referred to the shared TN/MS state quitline and provided the NCI “Clearing the Air” standard intervention.

An overview of Aims 1 and 2, which are now completed, is shown to the left.

Aim 1: Survey up to 1400 TN and MS SCCS smokers and up to 45 selected CHC providers to assess attitudes and beliefs on smoking-related health risk perceptions, precision smoking treatment, and willingness to engage in a smoking cessation trial of PC.

Aim 2: With continuous input from the CAB, develop two PC interventions, PC-NMR and PC-Respiragene, for use among diverse, low-socioeconomic status community smokers in the SCCS.

Aim 3: Conduct a 3-arm RCT to pilot PC interventions for feasibility and to determine preliminary estimates of biochemically-validated smoking cessation at 6 months vs. GBC. We hypothesize that, compared to GBC, PC participants will exhibit higher smoking cessation and lung cancer screening rates. (Illustration of Aim 3 is shown below on p. 8).

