All participants assigned to guideline based care (GBC) will be referred to the state quitline and will receive a smoking cessation intervention through the National Cancer Institute's (NCI) "Clearing the Air" program. Additionally, as part of clinical care, the primary care provider (PCP) will document guideline-based treatment recommendations and provide participants with prescriptions sufficient for a 3-month course of pharmacotherapy chosen at the clinical discretion of the provider. Written and verbal instructions will be provided to participants given medication to contact their primary provider and the research study staff (during regular business hours) to address any questions about medication. Participants will be instructed to call 911 if they believe they are having a medical emergency. GBC participants will also receive Respiragene and nicotine metabolite ratio (NMR) testing on their SCCS stored blood sample and will be informed of these results at the end of the study.

Respiragene Precision Care Group (PC-Respiragene)

All participants assigned to Respiragene precision care will receive guideline-based care, including a referral to the state quitline, as described above. Additionally, the PCP will have clinical decision support regarding the interpretation of the Respiragene test. Study staff will discuss results of the Respiragene test with the participant and the PCP will provide participants with prescriptions sufficient for a 3-month course of pharmacotherapy chosen at the clinical discretion of the provider based on guidelines relevant to differential health risks.

NMR Precision Care Group (PC-NMR)

All participants assigned to NMR precision care will receive guideline-based care, including a referral to the state quitline, as described above. Additionally, the PCP will have clinical decision support regarding the interpretation of NMR from the study team. Using the NMR data, the PCP will discuss

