results with the participant and provide participants with prescriptions sufficient for a 3-month course of pharmacotherapy based on NMR results (NRT for “slow” metabolizers and non-nicotine smoking cessation medication (varenicline) for “fast/normal” metabolizers). Participants who do not wish to receive varenicline, may have the option of a higher nicotine patch dose that has been studied previously. In this previous study, there were no significant differences between treatment arms in the frequency of severe side effects and serious adverse events or blood pressure during treatment ($p > .10$).²²

Participants may receive prescriptions through their own pharmacies or through a mail order pharmacy.

Check-in phone calls

Study staff will call participants at approximately 2 weeks after the study results call, and again approximately 1- 2 months following the results call, to encourage medication adherence and assess self-reported tolerance. If additional communication is needed, a tobacco counselor can be available for extra calls.

Table 1: RCT Data Collection Table for Aim 3					
Follow up Assessments	B L	1 mo f/u	Informal Check-in (2)	3 mo f/u	6 mo f/u
Smoking status	X	X		X	X
Cigarettes per day	X	X		X	X
Health risk perceptions	X	X		X	X
Lung cancer screening	X	X		X	X
Notify of PC results*		X			X
Calls to support med		X	X	X	

Outcome assessment

Subject outcomes will be assessed via phone calls at approximately 1, 3, and 6 months, as shown in Table 1. At follow up, an RA who is separate from intervention staff will complete interviews assessing smoking behavior, medication use and self-reported side effects, patient health risk perceptions and attitudes toward the PC interventions, and whether the patient received a lung cancer screening. Participants reporting abstinence at six months will be mailed a standard salivary cotinine kit for biochemical validation of smoking abstinence, defined as ≤ 10 ng/ml.

adherence, tolerance					
CO-validated abstinence					X
*Participants in PC arms (Respiragene, NMR) notified of results; GBC participants are contacted to match for time					

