Adverse drugs reactions: Participants in this study may receive one of two FDA-approved smoking cessation therapies (NRT or varenicline) and will have the potential to experience drug-related side effects. Nicotine replacement therapy is generally very safe and several preparations of it have been sold over the counter for decades). However, possible side effects include, but are not limited to, skin irritation or itching (patch), dizziness, headache, nausea, mouth/throat irritation (inhaler/nasal spray), and rapid heartbeat. Common side effects of varenicline include nausea, sleep disturbance and vivid dreams, gastrointestinal symptoms, and vomiting. Very rarely, patients, particularly those with unstable psychiatric conditions, may experience symptoms such as behavioral changes, agitation, depressed mood, and suicidal behavior during varenicline treatment. In a large FDA-mandated trial (EAGLES, Lancet 2016) all three of these medications were found to be safe and effective in patients with and without pre-existing psychiatric conditions.²³ To protect against risk from pharmacotherapy usage, this study will only use FDA-approved smoking cessation medications and tobacco treatment providers will screen patients to identify contraindications to NRT or varenicline. Written and verbal instructions will be provided to patients given medication to contact their primary physician and the research PI, [name], in case of adverse effects of a medication. Additionally, study staff will call participants during active treatment to monitor for medication side effects. Ultimately, the PI ([name]) will review any serious adverse events and report them appropriately to the IRB.

8.0 Reporting of Adverse Events or Unanticipated Problems Involving Risk to Participants or Others

Any serious adverse events will be reported to the IRB and NIH according to appropriate policies and procedures. Serious adverse events are defined as untoward or undesirable medical events, related to study procedures, that 1) are of at least moderate severity as reported by participants at follow-up; 2) require hospitalization or ER visit; 3) are life-threatening or cause death or permanent impairment/disability; or 4) require intervention to prevent death or permanent impairment/disability.

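### Do the Aim 3 engagement measures lack a match in the trial procedures?

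*Combined protocol and SAP*

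**What the plan says.** Section 10.0 makes feasibility the primary outcome of the pilot and states that it is not powered for differences in cessation. Under the Aim 3 Primary Analysis it lists three engagement measures: "1) connection with the study tobacco treatment counselor, (2) connection with the state quitline and (3) use of study-provided medication". It then adds: "We will also collect information on process measures such as enrollment, educational material format, and costs per patient treated".

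Section 2.0 explains why engagement is of interest. The trial is to "determine preliminary estimates of PC interventions vs. standard guideline-based care (GBC) on engagement", and the expected effects are to be explained in part by "use of proven quit aids (medication, behavior therapy via state quit line").

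The procedures bearing on the three measures are these:

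- **Quitline.** Section 2.0 says: "All RCT participants are referred to the shared TN/MS state quitline". Section 6.0 repeats the referral for each arm.
- **Medication.** In the guideline-based arm the primary care provider is to "provide participants with prescriptions sufficient for a 3-month course of pharmacotherapy chosen at the clinical discretion of the provider". The provider also prescribes in the two precision care arms. Prescriptions are filled at the participant's usual pharmacy or by mail order.
- **Counselor.** Under Check-in phone calls (Section 6.0), scheduled calls are made by study staff, and a tobacco counselor can be called on if more contact is needed.
- **Follow-up.** At about 1, 3 and 6 months a research assistant outside the intervention team conducts "interviews assessing smoking behavior, medication use and self-reported side effects, patient health risk perceptions and attitudes toward the PC interventions", and also asks about lung cancer screening.

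**The concern.** A measure named in the primary analysis should be traceable to something the trial records. Here the trace seems to break three times.

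Referral to the quitline is universal, so it cannot separate participants or arms; only actual contact can. Contact is not named among the interview topics, the rows of Table 1 or the named process measures. If nobody asked, one of the three engagement rates could not be reported, and one of the mechanisms proposed in Section 2.0 could not be examined.

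No study supply of medication is described. Section 7.0 remarks of nicotine replacement that "several preparations of it have been sold over the counter for decades". Unless the source is recorded, use of the prescribed course and use of any cessation product could be mixed.

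If the counselor is reached only when extra help is needed, counting those calls would partly measure need instead of engagement. Connection is not defined for any measure, and no denominator is given.

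**Working it through.** No formula applies, and the plan gives no figure to reproduce. The check is to set each measure beside what the document says is done and recorded.

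| Measure (Section 10.0) | Procedure described | Recording described |
|---|---|---|
| Counselor connection | Scheduled calls by study staff; counselor on call for more (Section 6.0); contraindication screening by tobacco treatment providers (Section 7.0) | Support calls have a row in Table 1 |
| Quitline connection | Referral of every participant (Sections 2.0 and 6.0) | None named |
| Medication use | Prescription by the primary care provider, own or mail order pharmacy (Section 6.0) | Named topic of the 1-, 3- and 6-month interviews |

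**Medication.** The data exist, because use is asked about at each follow-up interview. What does not fit is the label of study provision. Section 6.0 uses the heading of medication provision for the prescription pathway, so the label can be read as loose wording for medicine obtained through the trial. The over-the-counter point starts from a safety remark in Section 7.0 and adds the assumption that source is not asked. The document does not settle that either way.

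**Counselor.** Reading this contact as purely optional requires that study staff exclude the counselor, which the text never says. Table 1 schedules support calls at 1 month, at the two informal check-ins and at 3 months. Section 7.0 gives tobacco treatment providers a screening task that is not conditional. Whether any of these people is the counselor named in Section 10.0 is unclear. The role is therefore undefined. The plan nowhere says that only the extra calls count.

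**Quitline.** Contact is absent from three lists: 7 rows in Table 1, 6 interview topics and 3 named process measures, or 7 + 6 + 3 = 16 labels. That count carries little weight, for four reasons.

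1. The lists overlap. Smoking, risk perception and screening each appear both in Table 1 and among the interview topics.
2. Two of the 7 rows (notification of results and support calls) are procedures, not data items.
3. Table 1 is demonstrably incomplete, since medication use is an interview topic without a row of its own. The process list is given as examples only.
4. The interview list is one sentence of topics. Smoking behavior could well cover quit aids: Section 1.0 places use of quit aids and quit attempts among the smoking-related questions of the parent cohort's third follow-up survey.

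Point 4 does not prove that a quitline item exists, but it shows that the lists cannot establish that none does. The questionnaires are not in the document and Figure 2 is not shown. The document also does not say whether the referral returns any report of contact, so the interview need not be the only source.

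**Consequence.** With up to 100 participants allocated 1:1:1 (100 / 3, about 33 per arm), the engagement results are descriptive rates. Section 10.0 attaches no test and no threshold to them. Validated cessation and screening have their own recording, in the follow-up interviews and Table 1, and do not depend on these definitions.

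**The case for a change.** The strongest case for a change is the quitline. Feasibility is the primary outcome, engagement is the first item under the Aim 3 Primary Analysis, and Section 2.0 promises estimates of it. The other quit aid, medication, also lacks a Table 1 row but is at least named in the interview text; quitline contact is named in neither. Asking would cost one short question in calls already scheduled, and if the question is missed, no other source is planned in the text. There is also an asymmetry in staff contact: study staff discuss results in the Respiragene arm and the provider does so in the NMR arm, while a footnote to Table 1 says guideline-based contacts are matched for time. A count of staff calls would need one definition across arms.

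Much of this stands as description. The source of the quitline measure is not stated, connection is not defined, and the medication label does not fit the supply described. It does not establish that quitline contact is uncollected or unrecoverable, because Section 10.0 itself commits the team to measuring it and the instruments that would carry it out are not visible.

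The natural repair for the counselor measure, counting completed scheduled calls, has its own hazard. If the 1-, 3- and 6-month outcome interviews were included, engagement would become retention. Rewriting that measure before knowing who the counselor is could make it worse.

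**Conclusion.** No change to the plan follows. The medication part is a wording slip over data already collected. The counselor part is an undefined term. The quitline part is an unstated data source for a measure the plan has undertaken to report. Staff building the questionnaires and analysts preparing the tables would be expected to settle all three: where quitline contact is recorded, that medication use means self-reported use at follow-up, which calls count as counselor contact, and what the denominator is.

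The possible loss is confined to descriptive engagement rates in up to 100 participants and to the quitline part of an exploratory explanation. No test, threshold, cessation estimate or screening estimate is affected.

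This rests on one assumption that the document cannot confirm: that quitline contact is captured, either in the follow-up questionnaires or through a report from the quitline. If neither held, that single rate would be missing, and the point would deserve more weight.
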